5. PLANNED ANALYSES

5.1. Interim Analyses

A Data and Safety Monitoring Board (DSMB) will be responsible for ongoing monitoring of safety for the study. The DSMB members are independent of the study team and are external to the Sponsor. Unblinded analyses will be prepared and provided to the DSMB by an independent statistical group at the contract research organization (CRO). A DSMB charter describes the role of the DSMB in more detail.

Efficacy and futility interim analyses were planned at the beginning of this study but were removed due to fast enrollment such that the final sample size was reached prior to the first planned interim analysis.

5.2. Final Analyses

6. FINAL ANALYSES WILL BE PERFORMED AFTER DATABASE LOCK WHEN ALL SUBJECTS HAVE COMPLETED OR DISCONTINUED FROM THE STUDY AND DATA CLEANING HAS BEEN COMPLETED. GENERAL CONSIDERATIONS FOR DATA ANALYSES AND HANDLING

6.1. General Summary Table and Individual Subject Data Listing Considerations

Unless otherwise specified, continuous variables will be summarized by using the number of non-missing observations, arithmetic mean, standard deviation (SD), minimum, first quartile, median, third quartile and maximum values as summary statistics; categorical variables will be summarized by using the frequency count and the percentage of subjects in each category as summary statistics. Descriptive summaries will be tabulated by treatment group.

When a summary tabulates the number of subjects, subjects will only be counted once for a category (e.g., a particular adverse event type, a particular adverse event term, a particular concomitant medication) unless otherwise specified.

All statistical tests will be performed at a 0.025 significance level using one-sided tests, unless otherwise noted. Statistical tests will use stratification factors (age and region) according to randomization. Stratification factors may need to be removed or have their levels combined so that low or zero counts in one stratum do not invalidate relevant statistical tests.

Unless otherwise specified, all efficacy and virology analyses will be performed on the modified intent-to-treat (mITT) analysis populations for each stratum. All safety analyses, demographics, and baseline characteristics will be performed on the safety population. Refer to Section 6.5 for details on analysis population definitions.

All Safety, Efficacy, and Tolerability data will be listed. In cases where additional information may be helpful, considerations for listings will be noted in this document.

6.2. General Post Text Summary Table and Individual Subject Data Listing Format Considerations

By-subject listings will be sorted by population stratum (i.e. supportive-care only, combination antiviral), antivirals used (for combination antiviral only), treatment, subject ID number, assessment/start date, and assessment/start time (where applicable). Subject identification will include age, sex, country (as 3-digit code) and race.

6.3. Data Management

Data management and cleaning will be conducted in accordance with the standard operating procedures (SOP) of the CRO for the study with oversight in accordance with the Sponsor's corresponding SOP. Derived datasets, data analyses and summary tables will be created using SAS[®] software, version 9.4 or above.

Version 5 June 24, 2024

6.4. Data Presentation Conventions

Unless otherwise indicated, data summaries and individual listings will be presented by population stratum and treatment. Treatment will be considered as BEM and placebo within each population stratum. For presentations of efficacy analysis, subjects will be grouped according to the treatment to which they were randomized. For presentations on the safety analysis, subjects will be grouped according to the treatment that was received.

6.5. Analysis Populations

6.5.1. Screen Failures

Screen failures will include subjects who fail to meet inclusion/exclusion (I/E) criteria. Subjects who are enrolled and do not fail any I/E criteria but decide not to participate in the study prior to randomization will also be included here.

6.5.2. Safety Population

The safety population will include all subjects who received at least one dose of the study drug (BEM or placebo). The study population will be analyzed as treated. Any subjects who were randomized more than once will be excluded from the summary tables, but the data will be included in listings and indicated appropriately.

6.5.3. ITT Population

The intent-to-treat (ITT) population will include all randomized subjects and will be analyzed as randomized.

6.5.4. mITT Population

The modified intent-to-treat (mITT) population includes all randomized subjects who received \geq 1 dose of study drug and have \geq 1 positive SARS-CoV-2 result (from NP swab samples via central testing) through Day 5. The majority of subjects are expected to have the positive SARS-CoV-2 qualifying sample at baseline, but the window is extended to allow the inclusion of subjects who may have a baseline false negative (via central testing) or missing sample at baseline. Any subjects who were randomized more than once will be excluded from the summary tables, but the data will be included in listings and indicated appropriately.

The modified intent-to-treat-S (mITT-S) population includes all randomized subjects who received ≥ 1 dose of study drug, have ≥ 1 positive SARS-CoV-2 result (from NP swab samples via central testing) through Day 5, and who are stratified into the supportive-care-only population according to the standard of care received (i.e., per EDC).

The modified intent-to-treat-C (mITT-C) population includes all randomized subjects who received ≥ 1 dose of study drug, have ≥ 1 positive SARS-CoV-2 result (from NP swab samples via central testing) through Day 5, and who are stratified into the combination antiviral population according to the standard of care received (i.e., per EDC).

The mITT populations are further restricted from the ITT population, but the intent-to-treat principle has been maintained as the requirements only define the target population while not introducing bias between the two treatment arms. The mITT-S and mITT-C populations are

displayed separately to present the treatment comparisons in two different standard of care scenarios. If a subject is mis-stratified in randomization, actual stratification will be used in the analysis performed by strata.

6.5.5. Per Protocol Population

The per-protocol population for the supportive care population is a subset of the mITT-S population that:

- Received all 10 doses of study drug as per protocol (with the exception of those subjects who discontinued study drug to initiate remdesivir rescue therapy, or discontinued study due to hospitalization or death)
- Did not have any inclusion/exclusion criteria protocol violations.

Subjects are excluded from the mITT-S per-protocol population if they received non-study drugs with SARS-CoV-2 antiviral activity (e.g. nirmatrelvir/ritonavir, molnupiravir, favipiravir, monoclonal antibodies (mAbs)) for the current SARS-CoV-2 infection from screening (or 24 hours prior to randomization) through Day 29 (with the exception of non-study drugs administered as rescue antiviral therapy).

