5.6. Premature Treatment or Study Discontinuation

Subjects may voluntarily discontinue treatment or withdraw from the study at any time. They may also be removed from the study at the discretion of the investigator or Sponsor at any time. The investigator may withdraw a subject at any time if it is determined that continuing the study would result in a significant safety risk to the subject.

Premature treatment or study discontinuation may occur for any of the following reasons:

• Persistent noncompliance with the protocol requirements

- **AE**
- Death
- Subject request (withdrawal of consent)
- Investigator request
- Sponsor request
- Loss to follow-up
- Pregnancy

Individual Study Drug Stopping Rules

Study drug treatment will be immediately discontinued in any individual subject who experiences:

- Any treatment-emergent SAE, or AE of grade 3 severity or higher (including confirmed laboratory abnormalities of grade 3 severity or higher reported as AEs) considered by the investigator to be related to study drug
- Confirmed estimated glomerular filtration rate [eGFR] <30 mL/min/1.73 m²
- For subjects with liver function testing within normal limits on the Day 1 lab draw:
 - Confirmed treatment-emergent elevation of alanine aminotransferase (ALT) or aspartate aminotransferase (AST) > 3 x ULN with total bilirubin (TB) > 2 x upper limit of normal (ULN) not due to hemolysis, and without evident alternative cause for these elevations
- For subjects with ALT or AST levels above the upper limit of normal on the Day 1 lab draw:
 - Confirmed treatment-emergent elevation of ALT or AST > 3 x baseline with TB
 2 x ULN not due to hemolysis, and without evident alternative cause for these elevations
- For subjects with TB level above the upper limit of normal on the Day 1 lab draw:
 - Confirmed treatment-emergent elevation of ALT or AST > 3 x ULN with TB >2x baseline level (and not due to hemolysis), and without evident alternative cause for these elevations
- Initiation or planned initiation of remdesivir
- Pregnancy

Hospitalization for the acute management of COVID-19 or other medical conditions does not require discontinuation of study drug; however on-going study drug management will be at the discretion of the PI and treating physicians.

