Subjects who prematurely discontinue study drug treatment should be encouraged to remain in the study and maintain the same protocol schedule and assessments as described in Table 1. This will allow for continued subject follow-up for key outcome data. Subjects who prematurely

discontinue the study [prior to Day 29 (primary study period)] and are unable to maintain the same protocol schedule should complete early termination (ET) assessments at the time of study discontinuation, as described in Table 1. Nevertheless, all attempts should be made to contact the subject at Day 29 (telephone contact is acceptable) to confirm key study endpoints, including hospitalization and survival.

The primary study period is through Day 29. The end of the study for any individual subject will be defined as the 60-day follow-up contact.

5.7. Prior Therapy, Concomitant Therapy, Permitted Therapy, Cautionary Therapy, and Prohibited Therapy

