3.2.1. Primary Endpoints

The primary efficacy endpoint is the proportion of subjects in the supportive-care-only population who are hospitalized for any cause or died due to any cause through Day 29.

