8.6. Analysis of the Primary Efficacy Endpoint

Table 4:	Summary (of Analyses	Related to the	Primary Effic	cacy Endpoint
	•	•		•/	•

Analysis	Population	Handling of Intercurrent Events	Analysis Approach
Primary Analysis: All- cause hospitalizations and deaths (through Day 29)	mITT-S	Treatment policy	Cochran-Mantel-Haenszel
Supplemental Analysis: All-cause hospitalizations and deaths (through Day 29)	mITT-S Completers	Treatment policy	Cochran-Mantel-Haenszel
Supplemental Analysis: All-cause hospitalizations and deaths (through Day 29)	mITT-S Per-protocol	Treatment policy	Cochran-Mantel-Haenszel
Supplemental Analysis: All cause hospitalizations and deaths (through Day 29)	mITT-S	Intervention with COVID-19 rescue as event (composite handling); Treatment policy otherwise	Cochran-Mantel-Haenszel
Supplemental Analysis: Time to all cause hospitalization and death (through Day 29)	mITT-S	Intervention with COVID-19 rescue as event (composite handling); Treatment policy with censoring for early study discontinuation (prior to Day 29) without event	Kaplan-Meier plot, stratified logrank test

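### The per-protocol exception in SAP 6.5.5 is tied to leaving the study, so a non-fatal hospitalization during dosing can drop out of the analysis because the subject stayed in follow-up

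*SAP*

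**What the plan says.** SAP 6.5.5 defines the per-protocol set as a subset of mITT-S. The dosing condition is "Received all 10 doses of study drug as per protocol". Two groups are excused from it: "those subjects who discontinued study drug to initiate remdesivir rescue therapy", and those who "or discontinued study due to hospitalization or death". The first exception concerns study drug; the second, as written, concerns the study.

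Protocol 5.6 treats stopping drug and leaving the study as different things. It states that "Hospitalization for the acute management of COVID-19 or other medical conditions does not require discontinuation of study drug", and that "on-going study drug management will be at the discretion of the PI and treating physicians". It adds: "Subjects who prematurely discontinue study drug treatment should be encouraged to remain in the study".

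The events named in the second exception are the components of the primary endpoint, which counts subjects "who are hospitalized for any cause or died due to any cause through Day 29" (SAP 3.2.1). SAP Table 4 (section 8.6) lists "mITT-S Per-protocol" as the population for one supplemental CMH analysis of that endpoint. The Completers set in SAP 6.5.6 also accommodates subjects with an event, but keeps anyone hospitalized or dead before Day 29 with no condition on leaving the study.

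**The concern.** The second exception appears intended to keep subjects whose course was cut short by an endpoint event. Because it is tied to leaving the study, it misses those who stop drug after a hospitalization and then do what the protocol asks, which is to stay in follow-up. Their events are lost through good retention, not through poor adherence.

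There is a second, smaller gap. The exception does not clearly say that the missed doses must have been caused by the event. A subject who stopped drug on Day 2 for another reason and died on Day 25 could be kept, while an event-free subject with the same missed doses is excluded.

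At stake is how far the per-protocol row can be read as support for the primary result. The design expects few events, so a handful of reclassified subjects would be visible in that row.

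**Working it through.** **1. The rule applied to five courses.** All are mITT-S subjects with no eligibility violation and no antiviral outside the study other than rescue.

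| Course | Ten doses? | Exception met? | In the set? |
|---|---|---|---|
| Hospitalized Day 3, completes ten doses | Yes | Not needed | Yes, event counted |
| Hospitalized Day 3, drug stopped for remdesivir | No | First | Yes, event counted |
| Hospitalized Day 3, drug stopped, no remdesivir, withdraws from study because of it | No | Second | Yes, event counted |
| Hospitalized Day 3, drug stopped, no remdesivir, followed to Day 29 | No | Neither | No, event lost |
| No event, same missed doses, no remdesivir | No | Neither | No |

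Rows three and four differ only in whether the subject left the study. A death during dosing is kept on a natural reading, because death ends participation. The events exposed are therefore non-fatal hospitalizations before dose ten, with drug stopped, no remdesivir, and the subject still in the study.

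**2. The plan's own figures.** Inputs from SAP 4.3.1 and 11.2: 4% placebo, 1.6% BEM, one-sided 0.025, 90% power, 1:1. With mean rate 0.028:

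n per arm = [1.960 × √(2 × 0.028 × 0.972) + 1.282 × √(0.04 × 0.96 + 0.016 × 0.984)]² / 0.024² = 991.

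That matches the SAP: 1982 in total. 1982 × 1.055 = 2091, stated as 2100; 2100 / 0.95 = 2210.5, stated as 2210. At 1050 per arm the expected events are 1050 × 0.04 = 42.0 placebo and 1050 × 0.016 = 16.8 BEM.

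**3. Equal loss in both arms.** The documents do not say what share of events falls before dose ten. Assumptions: share e from 10% to 40%, all of these lost, and 5% of event-free subjects incompletely dosed and excluded. For an arm with E expected events, the events kept are E(1 − e) and the denominator is 1050 − E·e − 0.05(1050 − E).

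Example at e = 20%. Placebo: 42.0 − 8.4 = 33.6 over 1050 − 8.4 − 50.4 = 991, or 3.39%. BEM: 16.8 − 3.4 = 13.4 over 995, or 1.35%. Nominal power is Φ{[d√n − 1.960√(2p̄q̄)] / √(p₁q₁ + p₂q₂)}. With d = 0.0204 and n = 993, this is Φ(1.03) = 0.848.

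| Share lost | Placebo events | BEM events | Relative risk | Nominal power |
|---|---|---|---|---|
| 0% | 42.0 | 16.8 | 0.40 | 0.915 |
| 10% | 37.8 | 15.1 | 0.40 | 0.886 |
| 20% | 33.6 | 13.4 | 0.40 | 0.848 |
| 30% | 29.4 | 11.8 | 0.40 | 0.799 |
| 40% | 25.2 | 10.1 | 0.40 | 0.737 |

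These overstate the loss for a given e, because deaths, remdesivir starters and hospitalized subjects who finish ten doses all stay in.

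**4. Unequal loss.** Take no true effect (4% in both arms) and the same 5%. If every early BEM event is lost and every early placebo event kept, the relative risk is 0.90, 0.81, 0.71 and 0.61 at e = 10, 20, 30 and 40%. At 40%: (25.2/983) / (42.0/1000) = 2.56% / 4.20% = 0.61. The reverse pattern gives 1.11 to 1.64. With 75% of early events lost in BEM and 25% in placebo, it is 0.95 to 0.78. These bound what the rule permits; they do not predict what will happen.

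**The case against.** The strongest reply is that the missing word is a slip. The parenthesis qualifies a dosing requirement, so the second exception can be read as stopping study drug. On that reading the dependence on leaving the study disappears. This is plausible, but the two exceptions use different words, and the documents keep the two dispositions apart (Protocol 5.6; the separate tabulations in SAP 7.1). A programmer following the text would exclude these subjects. A slip still has to be corrected.

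Second, excusing doses that an event prevented is reasonable, and any such rule lets a hospitalized subject qualify on fewer doses than an event-free one. That stands, and it applies to the fix too. The gain is one adherence standard up to the event, not independence from outcome. The existing wording can also be read as excusing only doses missed because of the event, so the second gap is one of clarity.

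Third, the exposed group is narrow. Hospitalization does not force a drug stop, missed doses are made up at the end of the course (Protocol 5.4.2), and subjects expected to need hospitalization within 24 hours are excluded (exclusion criterion 4). This stands.

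A reader might infer that a large share of the events, say a third to a half, would be gained or lost on disposition alone, and differently by arm. The documents support neither inference. They give no event timing, remdesivir use and death also decide inclusion, and sites and subjects are blinded. Differential loss is possible but not shown.

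**Conclusion.** The definition is wrong as written, and the severity is minor. Read literally, SAP 6.5.5 removes a non-fatal early hospitalization from the per-protocol analysis when drug is stopped without remdesivir and the subject stays in follow-up, and keeps the same event if the subject withdraws. It also leaves adherence before the event unclear.

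The number of events affected cannot be derived from the documents. Under the assumed 10% to 40% range, equal loss lowers the nominal power of this row from 0.915 to between 0.886 and 0.737, with the relative risk unchanged to two decimals. Unequal loss would bias it in either direction.

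The defect does not reach the primary mITT-S analysis, the type I error or the sample size. The per-protocol row is not in the testing sequence of SAP 8.5. The other Table 4 rows keep these hospitalizations, so a distortion would show when the rows are compared.

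**What to change.** Reconcile SAP 6.5.5 with Protocol 5.6 by two changes to the SAP:

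- In the second exception, refer to discontinuing study drug instead of discontinuing the study.
- Define dosing adherence for all subjects as having taken every dose due up to the earliest of hospitalization, death, start of rescue therapy or the tenth dose, regardless of whether the subject later stayed in the study.

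The cost is a wording change and one derivation from the dosing diary, which already records dose times (Protocol 5.4.3). Trial conduct does not change. SAP section 2 allows revision before unblinding. If the data are already unblinded, report the analysis under this definition beside the one under the current SAP text, and record it in the clinical study report as a deviation, as that section provides.

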6.5.6. Completers

Subjects considered as having completed the primary study follow-up are those in the mITT population who were followed through to at least Day 29 or had a hospitalization or death event prior to Day 29. Any subject who has a Day 29 (or subsequent scheduled) visit or an assessment on a date corresponding to study day 29 or later (see Section 6.7.2) will be considered as having been followed through to at least Day 29.

6.5.7. PK population

The PK population will include all subjects who receive at least 1 dose of AT-527 and have at least 1 pharmacokinetic measurement.

6.6. Baseline Definition

Baseline is defined as the last available assessment prior to first dose of study treatment (BEM or placebo). For analyses of virology data, if there is no pre-study drug assessment available then baseline can be up to 4 hours post first dose, with the earliest assessment within this time window used as baseline in the case of multiple qualifying assessments. For analysis of symptoms, Day 1 assessment will be used as the baseline.

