6.7. COVID-19 Symptom Assessment

A COVID-19 symptom diary will be completed daily until Day 29 (Table 1). The symptom diary is provided in Appendix 1 (Section 13.1). This diary will be used to characterize key symptoms recognized as part of COVID-19 illness based on FDA guidance (FDA 2020). The COVID-19

Symptom Diary is composed of individual symptom item questions, each with a 2- or 4- point Likert response option. In addition to symptoms, subjects will be asked for a self-assessment as to whether they have returned to their usual (pre-COVID-19) health status, as well as their assessment of COVID-19 symptom relapse.

On Day 1, a baseline diary questionnaire should be completed at the clinic, prior to the first dose of study drug. Thereafter, the COVID-19 Symptom Diary will be completed in its entirety by the subject once daily at the same time each evening through Day 29.

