6.7.4. Visit Windows

For the purposes of by-visit analyses for scheduled clinical assessments (i.e., excluding patientreported assessments), visit windows for inclusion in the analysis are defined in Table 3. Note that the definition of baseline is provided in Section 6.6.

Visit	Target Study Day	Visit Window, Study Day(s)		
Baseline/Day 1 ^a	1	1		
Day 3	3	2-4		
Day 5	5	4-6		
Day 7	7	7 – 10		
Day 14	14	11 – 21		
Day 29	29	22 - 36		
Day 60	60	>36		
a. If a Day 1 assessment is not available, a qualifying baseline assessment can be utilized.				

Table 3:Visit Windows (Days)

Patient reported outcomes are to be reported daily on Days 1-29 and data will be based on the corresponding day. If there is more than one assessment on a day, then the least favorable assessment will be utilized for analysis.

There is overlap at study day 4 for the Day 3 and Day 5 windows to increase the chance to have qualifying observations at both of these timepoints. In the case where a measurement is captured on Day 4, the assignment for the observation will be according to the following:

- If there is another measurement on study day 5 and:
 - Another qualifying measurement for Day 3: day 4 measurement not assigned to Day 3 or Day 5
 - Otherwise, day 4 measurement assigned to day 3 and day 5 measurement assigned to Day 5.
- Else if there is another measurement on study day 6 and:
 - Another qualifying measurement for Day 3: day 4 measurement not assigned to Day 3 or Day 5
 - Otherwise, day 4 measurement assigned to Day 3 and day 6 measurement assigned to Day 5.
- Else day 4 measurement is assigned to Day 5.

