8.8. Analysis of Exploratory Efficacy Endpoints

The following exploratory endpoints will be examined in both supportive care only and combination antiviral arms.

Time to sustained alleviation or improvement of COVID-19 symptoms

Sustained alleviation/improvement of COVID-19 signs/symptoms is defined as the first occurrence of 4 consecutive days when all symptoms recorded as moderate or severe at study entry are recorded as mild or absent and all symptoms scored mild or absent at study entry are scored as absent. The first day of the 4 consecutive-day period corresponds to the day that the event is achieved. The endpoint will be based on targeted symptoms, which are the 13 symptoms with severities ranging from none to severe in Item 3 of the COVID-19 symptom diary. Subjects who do not achieve the endpoint will be censored according to the following rules:

Case	LOD-3	LOD-2	LOD-1	Last Observed Day (LOD)	Censoring time
1	Not Met	Not Met	Not Met	Not Met	LOD+1
2	Not Met	Not Met	Not Met	Met	LOD
3	Not Met	Not Met	Met	Met	LOD-1
4	Not Met	Met	Met	Met	LOD-2

The cumulative distribution function for time from Day 1 to sustained alleviation/improvement of symptoms will be estimated by Kaplan-Meier methodology and plotted by treatment group. The summary display will include the Kaplan-Meier estimates of proportion achieving the endpoint by day. The analysis will also be carried on subgroups of time from onset of symptoms (<=3 days, > 3days).

Sensitivity analysis will be carried using the same methods for 2 selected subsets of symptoms: 1) runny/stuffy nose, sore throat, cough, feeling hot or feverish, and fatigue; 2) runny/stuffy nose, sore throat, shortness of breath, feeling hot or feverish, headache, and chills; 3) all symptoms from Item 3 of the COVID-19 symptoms diary except fatigue.

Additional subgroup analyses on age group (<65 and >=65), and symptom onset days (<=3 days and >3 days) for time to sustained alleviation of all 13 symptoms will be performed.

Time to self-reported return to usual (pre-COVID-19) health

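### SAP 6.6 and 6.7.4 together let a post-dose Day 1 diary become the symptom baseline, which can loosen the target of the exploratory alleviation endpoint

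*SAP*

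**What the plan says.** Five sets of rules bear on this point.

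- **Baseline (SAP 6.6).** The general rule is the last record before the first dose. Two exceptions follow. Virology may use a post-dose sample, but only within 4 hours and only the earliest. For the diary the text reads "For analysis of symptoms, Day 1 assessment will be used as the baseline", with neither a pre-dose condition nor a time limit.
- **Study day (SAP 6.7.2).** It is computed from dates alone, so any diary dated on the day of first dose is a Day 1 diary, whatever the hour.
- **Several diaries on one day (SAP 6.7.4).** "Patient reported outcomes are to be reported daily on Days 1-29 and data will be based on the corresponding day". Then: "If there is more than one assessment on a day, then the least favorable assessment will be utilized for analysis". Day 1 is within the stated range and is not exempted.
- **Diary schedule (Protocol 6.7).** "On Day 1, a baseline diary questionnaire should be completed at the clinic, prior to the first dose of study drug". After that the diary is to be "completed in its entirety by the subject once daily at the same time each evening through Day 29". The text does not say whether the first evening diary falls on Day 1 or Day 2. Table 1 shows the diary daily on Days 1–29.
- **Endpoint (SAP 8.8).** Sustained alleviation needs 4 consecutive days on which symptoms that were moderate or severe at entry are mild or absent, and "all symptoms scored mild or absent at study entry are scored as absent".

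**The concern.** The alleviation target depends on the baseline, so the baseline should be fixed before treatment. The virology exception limits a post-dose baseline to a short window; the symptom exception has no such limit. A programmer who follows SAP 6.6, 6.7.2 and 6.7.4 literally would pool all diaries dated Day 1 and keep the worst.

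Protocol 5.4.2 has a subject whose first dose is before 16:00 take a second dose the same evening. A Day 1 evening diary could therefore follow one or two doses. A symptom that worsened after dosing would then be given an easier target, and a post-randomization value would help define the endpoint.

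At stake is how the exploratory time to sustained alleviation can be interpreted, together with its analyses by age group and time from symptom onset and on subsets of symptoms.

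**Working it through.** The plan gives no figure to reproduce. The check is to apply the rules to every possible case.

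**Route 1: two Day 1 diaries.** Inputs: the four severity levels (diary, SAP 11.1), the least-favorable rule (SAP 6.7.4) and the target rule (SAP 8.8).

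- Baseline = the worse of the pre-dose and evening severity.
- Target = absent if baseline is absent or mild; mild or absent if baseline is moderate or severe.
- Compare this target with the one set by the pre-dose value alone.

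| Pre-dose (rows), evening (columns) | absent | mild | moderate | severe |
|---|---|---|---|---|
| absent | same | same | looser | looser |
| mild | same | same | looser | looser |
| moderate | same | same | same | same |
| severe | same | same | same | same |

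Of 4 × 4 = 16 pairs, 4 loosen the target, 0 tighten it and 12 leave it unchanged. These are counts of cases, not probabilities. Only a crossing from absent or mild to moderate or severe matters; absent to mild, or moderate to severe, changes nothing.

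The table assumes that the worse record is chosen symptom by symptom. The SAP does not say whether the choice is made per item or per whole diary. If a whole diary were chosen, an item that was better in that diary could move the other way.

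**Route 2: clinic diary missed.** The evening diary is then the only Day 1 record, and the least-favorable rule is not needed. With no baseline diary, SAP 6.8.5 would impute each missing symptom as mild, which carries the strict target. Against that imputation, an evening value of absent or mild leaves the target the same, and moderate or severe loosens it: 2 of 4 values loosen, 0 tighten. Against the unobserved pre-dose severity the error could go either way.

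**With the baseline restricted to pre-dose diaries.** In Route 1, 0 of 16 pairs change the target. In Route 2 the SAP 6.8.5 imputation applies.

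**Size.** The documents do not say how many subjects would have a second Day 1 diary or how often a symptom would cross by evening. As an illustration on assumed values only, let each of the 13 scored symptoms have probability q of crossing, independently. The share of subjects with two Day 1 diaries who have at least one loosened target is 1 − (1 − q)^13:

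- q = 1%: 12%
- q = 2%: 23%
- q = 5%: 49%
- q = 10%: 75%

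The range is too wide to support an estimate, and it says nothing about a difference between arms.

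**The case against.** **The Day 1 assessment is the clinic diary.** Protocol 6.7 and 6.7.1 place the Day 1 diary before dosing. The opening of Protocol 6 and the notes to Table 1 say the same of Day 1 assessments generally. One diary per day, with evening diaries after the clinic one, can be read as starting on Day 2. SAP 8.8 speaks of severity at study entry. The SAP 6.6 sentence may serve only to prefer the Day 1 diary over the pre-existing symptom assessment at screening.

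Much of this stands. A reader might infer that the SAP sets the symptom baseline as the worst Day 1 diary. It does not say so, and a second Day 1 diary is permitted rather than clearly scheduled. But the protocol passages govern when diaries should be completed. They do not tell the analyst which record to use when a later one exists or the clinic one is missing. SAP 6.6 and 6.7.4 do, without a pre-dose condition.

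**Bias in favor of BEM.** Nausea, vomiting and diarrhea are among the 13 items, and Protocol 1.2.1 reports drug-related gastrointestinal events of 9.2% on BEM against 1.4% on placebo in the earlier Phase 3 study. A reader might infer that side effects would loosen the target more often on BEM. The documents do not support that step.

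- The excess in drug-related events is 9.2 − 1.4 = 7.8 points. The same section gives all gastrointestinal events as 11.3% against 9.9%, an excess of 1.4 points. A diary records symptoms whatever their cause, so the second figure is the more relevant.
- If 10–30% of the excess began on Day 1 at moderate severity (an assumption), the result is 0.8 to 2.3 points on the first figure and 0.14 to 0.42 on the second.
- No vomiting was reported on BEM, abdominal pain is not a diary item, and mild events cannot loosen a target. The day of onset is not given.

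**A looser target is not a changed outcome.** All targeted symptoms must meet their criteria on 4 consecutive days. Relaxing one item changes the event time only if that item was the limiting one. This stands.

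**Conclusion.** The concern holds as a gap in the record-selection rules. As written, the SAP allows a post-dose diary to serve as symptom baseline when a subject has a second, worse diary on Day 1 or has no clinic diary. With item-by-item selection, the effect on the target runs one way: 4 of 16 severity pairs loosen it and none tighten it. For a missed clinic diary, the same direction holds relative to the SAP's own imputation.

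The frequency, the effect on time to alleviation and any difference between arms cannot be derived from the documents, and no bias toward either arm is shown.

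The consequence is limited. The endpoint is exploratory (SAP 3.2.3), is absent from the testing sequence in SAP 8.5, and is analyzed in SAP 8.8 by Kaplan-Meier estimation. The primary endpoint does not use the diary. Symptom relapse, the only secondary endpoint that does, rests on diary question 4 and not on baseline severity.

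**What to change.** In SAP 6.6, define symptom baseline as the last diary completed before the first dose, with the existing SAP 6.8.5 baseline imputation if there is none. In SAP 6.7.4, state that post-dose diaries on Day 1 are not used for baseline and that the least-favorable rule applies from Day 2. It would help to add whether that rule works per symptom or per diary.

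The cost is about one sentence in each section and a small change to the derivation program. No new data are needed: the diary form has a completion time (SAP 11.1) and the dosing diary records dose times (Protocol 5.4.3). The change belongs in the SAP before unblinding.
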